1.0 SCHEMA

1.1 Correlative studies: Specimens required for eligibility:

- 1.1.1 Tumor sample collected from diagnostic biopsy (pre-neoadjuvant chemo)
- 1.1.2 Tumor sample collected from surgery (post-neoadjuvant chemo)

2.0 SYNOPSIS

2.1 Primary Objective:

To determine the feasibility of patients enrolling and receiving either postoperative chemoradiation or chemotherapy alone, based upon nodal status at surgery, following preoperative chemotherapy.

2.2 Secondary Objectives:

To evaluate the rate of cancer recurrence in patients assigned to treatment based upon node status

To explore the potential correlation between changes in expression of a pre-specified panel of genes identified as relevant to gastrointestinal cancers in response to preoperative chemotherapy, using presence of nodal involvement at time of surgery as an indicator of response.

2.3 Primary Endpoint:

The proportion of patients who would meet the criteria would be estimated to demonstrated successful enrollment and treatment of therapies including postoperative chemotherapy or chemoradiation as indicated by the nodal features, which would justify development of a study powered to demonstrate survival benefit to patients using this approach. Expect that no more than 30% of patients will be unable to complete all protocol therapy.

2.4 Secondary Endpoints:

The recurrence rate while on trial will be reported for the two arms of the trial, and compared to historical controls

Observation of changes in gene expression as a response to chemotherapy, categorized based upon correlation to nodal status. Expect that no more than 10% of tumors will be unable to have tumor assessed on both pre- and post- chemotherapy tumor specimens.

2.5 Study Design:

Open-label, stratified, two arm design. All patients receive same initial standard preoperative chemotherapy and surgical resection. Patients will then be assigned to either standard postoperative chemotherapy if node negative at surgery or standard postoperative chemoradiation if node positive at surgery.

2.6 Number of Patients:

Forty patients.

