3.2 Rationale for Piloting Chemotherapy versus Chemoradiation

Historically, administration of postoperative adjuvant therapy of any type is challenging following gastrectomy. In both the MAGIC and in the MacDonald Intergroup trials, less than 50% of patients were able to complete the postoperative adjuvant therapy recommended.^{1,2} Given improvements in patient selection, surgical techniques, methods for accelerating recovery after surgery, and improved management of chemotherapy toxicity, it is reasonable to expect that many more patients are able to complete these recommended postoperative therapies in current practice. However, this has not been validated. The feasibilities of the individual components of the proposed approach in this protocol are established standards. However, the use of chemoradiation following both pre-operative chemotherapy and surgery as a standard recommendation, based upon an objective surgical finding, is novel. Typically, patients who receive post-operative chemoradiation have received no preoperative therapy. Thus, the administration of chemoradiation to a patient after surgery who received chemotherapy prior to surgery is experimental. Additionally, the treating physicians oftentimes elect to eliminate the radiation if they arbitrarily feel that the patient may not benefit from it. Assuming the rates of node positive disease mirror those observed in the MAGIC protocol's retrospective review⁸, then the majority of patients will receive the recommendation for chemoradiation. When recommended, the administration of postoperative radiation to chemotherapy following preoperative chemotherapy and surgery for this majority of patients with node positive disease may or may not be feasible, depending upon the patients' abilities to tolerate such therapy. If feasible, the ability to study the larger questions of outcomes will be possible; this needs to be known before such a larger study is entertained. Finding that such therapy is not feasible for routine recommendation and administration despite an objective surgical result suggesting it is indicated would necessitate development of a trial of an alternative intervention for the management of these patients who have an anticipated poorer outcome. Therefore, piloting the use of postoperative chemoradiation therapy to determine if this is a feasible recommendation for further exploration of benefit is warranted.

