5.0 SUBJECT ELIGIBILITY: Patient Initials (L,FM): _____

5.1 Inclusion Criteria:

- 1) Must have pathologically-proven adenocarcinoma of the stomach or gastroesophageal (GE)-junction, stage M0, as established by both imaging and surgical pathologic staging.

Imaging: Clinical stage of M0 will be established by either CT (chest with contrast and abdomen/pelvis with and without contrast), or CT/PET (skull base to mid-thigh). This is standard post-surgery imaging.

Surgery: Surgical pathologic staging must be M0.

- 2) Must have completed 3 cycles of neo-adjuvant chemotherapy. Either CAPEOX or

FOLFOX is allowed. Dose modifications are allowed, but all 3 cycles must have been completed.

- 3) Must have undergone a surgical resection with definitive intent, either by open or laparoscopic resection of the primary gastric or GE junction cancer. Patients must have undergone a total gastrectomy, subtotal gastrectomy, or distal gastrectomy (depending on the location of primary gastric lesion) with at least a modified D2 lymphadenectomy.
- 4) Must be deemed as a good candidate for adjuvant chemotherapy or chemoradiation (to start within 3 months of surgery), in the opinion of the treating investigator. Plan must be to start adjuvant therapy within 90 days of surgery; adjuvant treatment cannot begin more than 90 days after surgery.
- 5) Must have diagnostic biopsy tissue (pre-neoadjuvant chemo) available for genetic testing.
- 6) Must have surgical tissue (post-neoadjuvant chemo) available for genetic testing.
- 7) Must be ≥ 18 years of age.
- 8) Must be able to provide informed consent.
- 9) Must have adequate kidney, liver, and bone marrow function, within 28 days prior to registration, as follows:
 - i. Hemoglobin ≥ 8.0 gm/dL
 - ii. Absolute neutrophil count (ANC) ≥ 1500 cells/mm³
 - iii. Platelet count $\geq 75,000$ /mm³
 - iv. Calculated creatinine clearance of > 60 mL/min/m², calculated as follows:
For males = $\frac{(140 - \text{age [years]}) \times (\text{body weight [kg]})}{(72) \times (\text{serum creatinine [mg/dL]})}$
For females = $0.85 \times$ male value
 - v. Total bilirubin ≤ 1.5 times upper limit of normal (ULN)
 - vi. AST (SGOT) and ALT (SGPT) ≤ 3.0 times the ULN
- 10) Must have life expectancy of greater than 3 months.
- 11) Must have an ECOG performance status 0-2.

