8.0 CRITERIA FOR STUDY CONTINUATION OR DISCONTINUATION

All patients who are enrolled on the study and begin any of their intended post-operative adjuvant therapy will be counted as evaluable for the study. This inclusion will be regardless of how much of the postoperative treatment they ultimately receive.

Criteria for discontinuation of post-operative treatment will be:

- a) Unacceptable toxicity
- b) Treatment delay due to toxicity > 2 weeks.
- c) Treatment delay for any other reason > 3 weeks.

Patients who discontinue treatment for these reasons will remain on protocol and will move on to surveillance/follow-up for disease recurrence

Disease recurrence, will be defined as radiographic tumor evidence detected by surveillance imaging. Confirmation of recurrence by biopsy will be at the discretion of the treating physician.

If a subject has disease recurrence during surveillance / follow-up, then further study follow-up can be discontinued; the subject will come off-study, and can be followed per standard clinical care at the investigator's discretion.

The patient may withdraw from the study at any time for any reason. Similarly, an investigator may remove a patient from the study for non-compliance with study protocol at any time. Patients removed from the study for these reasons will be replaced.

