10.0 STATISTICAL CONSIDERATIONS

The primary objective is to determine the feasibility of patients enrolling and receiving either postoperative chemoradiation or chemotherapy alone, based upon nodal status. Based on our experience, we projected that the eligible patients would receive chemoradiation or chemotherapy alone in 3:1 ratio after surgery. We designed this pilot study on 30 patients who receive chemoradiation and on 10 patients who receive chemotherapy alone based upon nodal status at surgery, for a total of 40 patients. At 50% of complete rate, the confidence intervals will have widths of a most +/- 17% and +/- 26.5% (confidence intervals calculated using Wilson method). For control purposes, no more than 30% of patients with node negative disease should be unable to receive postoperative chemotherapy. In order for postoperative chemoradiation to be a feasible recommendation in patients who have lymph node positive disease at time of surgery after preoperative chemotherapy, a majority of patients must be able to receive this chemoradiation in its entirety.

The primary endpoint is the proportion of patients who complete the recommended therapies as indicated by their surgical nodal status. The primary endpoint will be evaluated when the last patient completes the postoperative chemotherapy or chemoradiation assigned. Descriptive and summary statistics will be computed for demographics and clinical data of all patients enrolled in the study. In each group, complete rates will be summarized with a point estimate and 95% confidence interval (Wilson method). If no more than 30% of patients are unable to complete all protocol therapy, then this will be considered a feasible treatment for these patients.

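### The primary objective covers enrolling and receiving therapy, but the endpoint and its only decision rule measure completion, and registered patients who never start are not counted

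*Combined protocol and SAP*

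**What the plan says.** **Objective.** Section 2.1 reads "To determine the feasibility of patients enrolling and receiving either postoperative chemoradiation or chemotherapy alone", with treatment set by nodal status. Section 10.0 repeats it: "The primary objective is to determine the feasibility of patients enrolling and receiving either postoperative chemoradiation or chemotherapy alone, based upon nodal status".

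**Endpoint, synopsis.** Section 2.3 reads "The proportion of patients who would meet the criteria would be estimated to demonstrated successful enrollment and treatment of therapies". It names enrolment but does not say what the criteria are or who forms the denominator. It adds that success would justify a later study powered for survival.

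**Endpoint and rule, statistics section.** Section 10.0 narrows this: "The primary endpoint is the proportion of patients who complete the recommended therapies as indicated by their surgical nodal status". The one decision rule is "If no more than 30% of patients are unable to complete all protocol therapy, then this will be considered a feasible treatment for these patients". The same section puts a 30% ceiling on node-negative patients who cannot receive postoperative chemotherapy.

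**Who is counted.** Section 8.0 describes patients who are "enrolled on the study and begin any of their intended post-operative adjuvant therapy will be counted as evaluable for the study", however much treatment they go on to receive.

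**Who is registered.** Under Section 7.0, eligibility review, registration and arm assignment all follow surgery. By then, under Section 5.1, the patient has completed three preoperative cycles and has both tissue samples available. Item 4 adds "Must be deemed as a good candidate for adjuvant chemotherapy or chemoradiation", with a start planned within 90 days of surgery.

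**The concern.** The objective asks two things: whether patients can be enrolled into nodally assigned treatment, and whether they can receive it. The plan has a measure for the second only. No section gives an enrolment numerator, denominator, target rate or criterion, and no screening log is described.

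The second half is also measured on a reduced group. Up to 90 days may pass between surgery and the start of treatment. A patient who registers and then never begins has failed to receive the assigned therapy, yet falls outside the evaluable group that Section 8.0 describes. The Section 10.0 ceiling on patients who cannot receive chemotherapy would then omit those who received none.

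What is at stake is the pilot's main output. A feasibility conclusion used to justify a larger study could be drawn with no data on enrolling, and with registered non-starters left out of the deciding proportion.

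**Working it through.** **1. The plan's own figure.** Section 10.0 gives Wilson 95% half-widths of at most 17 points (n = 30) and 26.5 points (n = 10) at 50% completion. The formula is

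h = z·√[p(1−p)/n + z²/(4n²)] / (1 + z²/n), with z = 1.96 and p = 0.5.

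- n = 30: 1.96 × √(0.00833 + 0.00107) / 1.128 = 0.168, or 16.8 points.
- n = 10: 1.96 × √(0.02500 + 0.00960) / 1.384 = 0.263, or 26.3 points.

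Both agree with the plan. They describe the precision of completion only; no precision is planned for enrolment.

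**2. Objective against measure.**

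| Part of the objective | Measure | Denominator | Criterion |
|---|---|---|---|
| Enrolling | none | none | none |
| Receiving | completion proportion (Section 10.0) | not stated there; starters, from Section 8.0 | at most 30% not completing |

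**3. Effect of leaving out registered non-starters.** Take results exactly at the 30% limit among starters and add one registered patient who never starts.

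| Group | Among starters | Among registered, one non-starter | Not completing |
|---|---|---|---|
| Node positive | 21/30 = 70.0% (Wilson 95% 52.1 to 83.3%) | 21/31 = 67.7% | 10/31 = 32.3% |
| Node negative | 7/10 = 70.0% (39.7 to 89.2%) | 7/11 = 63.6% | 4/11 = 36.4% |
| All | 28/40 = 70.0% (54.6 to 81.9%) | 28/41 = 68.3% | 13/41 = 31.7% |

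In each row one non-starter moves the result from meeting the rule to missing it.

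More generally, completion among registered = completion among starters × share of registered who start. The documents give no start rate. Over an assumed range of 80 to 100%:

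- 0.70 × 0.80 = 56%
- 0.70 × 0.90 = 63%
- 0.70 × 1.00 = 70%

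**4. What a log would add.** The documents give no number screened, so these totals are assumptions. With 40 enrolled:

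| Screened | Enrolled/screened | Wilson 95% interval |
|---|---|---|
| 45 | 88.9% | 76.5 to 95.2% |
| 58 | 69.0% | 56.2 to 79.4% |
| 80 | 50.0% | 39.3 to 60.7% |
| 134 | 29.9% | 22.8 to 38.1% |

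These imply very different answers on enrolment, and the planned analysis could not tell them apart. Intervals within a nodal group would be wider.

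**The case against.** The best defence is that the working question is tolerability. Section 3.2 asks whether chemoradiation, when it is recommended, can be tolerated, and Section 10.0 wants a majority able to receive it in full. Entry limited to suitable candidates fits that question. This stands as a reason for the eligibility rule and supports narrowing the objective as one remedy. It does not explain why the objective names enrolling twice and Section 2.3 promises successful enrolment.

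Enrolment is not wholly untracked. Section 11.0 has the Data Review Committee monitor it, and Section 10.0 summarises baseline data for everyone enrolled, so the number of non-starters could be recovered. That is right, but the first is oversight without a target, and the second does not feed the endpoint or the rule. Reaching 40 patients shows that accrual happened, at an unstated pace from an unstated pool.

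Section 10.0 does not state its denominator, so a sponsor could read non-starters as patients unable to complete. Section 8.0 points the other way, and the text should settle it.

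A reader might go further in three ways that the documents do not support:

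- **Completion among all operated patients.** Multiplying 70% by a guessed share of operated patients who register and start, and setting the product beside the history in Section 3.2 ("less than 50% of patients were able to complete the postoperative adjuvant therapy recommended"), does not work. The share has no source. Both postoperative treatments are described as standard, so a patient who declines the trial may complete treatment off study.
- **Different denominators from the historical trials.** Section 3.2 does not give theirs, and the plan tests completion against a fixed limit, not against that history.
- **Failure of the larger trial to recruit.** Its eligibility and accrual needs are not described.

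**Conclusion.** The point holds as a mismatch between objective and measure. As written, the plan cannot answer the enrolment half of its primary objective, and registered patients who never start do not count against feasibility. The second part rests on taking the denominator from Section 8.0, because Section 10.0 is silent.

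The size is uncertain because the documents give neither a start rate nor a screening count. At the 30% limit, one registered non-starter reverses the result in either group or overall. If 80 to 100% of registered patients start (assumed) and 70% of starters complete, completion among registered patients is 56 to 70%. If nearly all registered patients start and completion is well above 70%, the second part makes little difference; the enrolment gap remains. The planned sample size and its precision figures are unaffected.

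**What to change.** 1. In Section 10.0, state that the denominator for completion is all registered patients. Report started/registered and completed/registered by nodal group with Wilson 95% intervals, and align the evaluable definition in Section 8.0.
2. Keep a de-identified log of patients screened after resection following the required preoperative chemotherapy, with nodal status and the reason for not registering. Report registered/screened by nodal group with Wilson 95% intervals. State an enrolment criterion in advance beside the 30% completion rule. The documents give no basis for its value, so the sponsor must choose and justify one.
3. If no log is kept, restrict the objective in Sections 2.1 and 10.0, the endpoint in Section 2.3 and the conclusion to completion of assigned therapy among enrolled patients. Item 1 still applies.

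The cost is modest extra data collection, with no added trial patients or procedures. The log needs a clear definition of its pool, since the protocol does not say where surgery takes place, and an agreed basis for recording limited data on patients who do not consent. Counting all registered patients may also give a less favourable completion figure.

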Unfortunately, knowing which tumors will respond better to which therapy remains unpredictable. Certain clinical features can help clinicians to make a recommendation for their adjuvant approach. For example, patients who have tumors that are symptomatic, such as with bleeding or gastric obstruction, are less likely to tolerate several months of surgical delay while chemotherapy is administered preoperatively, and thus will typically be offered upfront surgery, followed by adjuvant chemoradiation. For most patients, however, the administration of systemic therapy prior to surgery as a part of a perioperative approach is recommended. This approach is favored because of the local control and reduction in tumor that can result prior to surgery, which is thought to lead to better outcomes in the long term.

However, not all patients will experience a response to preoperative chemotherapy. In those patients whose tumors are found at surgery to remain advanced, with nodal involvement, despite preoperative chemotherapy, long-term outcomes have been shown to be poorer than those whose tumors responded well, with the absence of nodal involvement upon dissection.⁸ These data are based upon the retrospective analysis of those patients who were enrolled in the original MAGIC study. Approximately 75% of tumors were found to be in the category of having nodes involved with cancer at resection despite preoperative chemotherapy. Thus, for this majority of patients with gastric cancer who have an inadequate response to preoperative chemotherapy (i.e., who remain node-positive at surgery), an alternative approach to their postoperative adjuvant treatment rather than mere completion of postoperative chemotherapy is apparently necessary.

One reasonable alternative for the management of patients who remain node positive at surgery

could be to incorporate radiation into their postoperative adjuvant treatment. There is some evidence for this approach, coming from the South Korean ARTIST trial.^{9,10} In the ARTIST trial, patients who underwent gastrectomy for stomach cancer randomly received either post-operative chemotherapy or chemoradiation therapy. Although no overall survival benefit was seen overall in the ARTIST study, in subset analysis, node positive patients had a significant improvement in disease-free survival with adjuvant chemoradiotherapy versus adjuvant chemotherapy alone.

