4.3 Genetic profile correlative studies

- 4.3.1 All patients will have undergone two tumor tissue acquisitions during standard clinical practice. Specimens from these acquisitions must be available:
- Prior to initiation of preoperative chemotherapy, tumor tissue will be obtained from the diagnostic biopsy samples;
 - Tumor tissue will be obtained at the time of surgery.

Both of these samples will be a part of standard of care, thus no additional biopsies beyond this standard will be performed for the study.

A preselected panel of genetic markers will be assessed for expression within each sample, and compared for differences, pre- and post-chemotherapy. These differences will be correlated for any response in tumor, i.e., node positive versus node negative.

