6.0 CLINICAL AND LABORATORY EVALUATIONS

6.1 Screening / Baseline Evaluation

- 6.1.1 Diagnostic (biopsy) and surgical confirmation of adenocarcinoma of gastric or GE junction origin; samples to be used for genetic profile.
- 6.1.2 A medical history and physical exam (H&P) to include the following information:
 - 6.1.2.1 A signs and symptoms assessment, including history of weight change
 - 6.1.2.2 Complete physical exam, including the following: vital signs, height, weight, and ECOG performance status.
 - 6.1.2.3 Baseline Toxicity Assessment
- 6.1.3 Laboratory studies must be obtained within 28 days (unless noted otherwise) prior to registration, to include the following:
 - 6.1.3.1 Complete blood count (CBC) with differential and platelets.
 - 6.1.3.2 Serum chemistries: liver enzymes (AST, ALT, alkaline phosphatase), blood urea nitrogen (BUN), creatinine, electrolytes (sodium, potassium, chloride, calcium, bicarbonate), total protein, albumin, total bilirubin, and glucose.
 - 6.1.3.3 For women of child bearing potential, a serum β -HCG pregnancy test.

- 6.1.4 Tumor imaging with either CT (chest with contrast and abdomen/pelvis with and without contrast) or CT/PET (skull base to mid-thigh); must be within 42 days of treatment start.
- 6.1.5 Pathologic evaluation of tumor specimen will include standard lymph node evaluation. Nodal disease will be classified into one of two categories:
 - lymph node negative, where no nodes are involved with tumor, or lymph node positive, where one or more nodes are involved with tumor.

6.2 Arm 1: Adjuvant Chemotherapy: Evaluation of patients deemed lymph node negative at time of surgery and treated with postoperative chemotherapy:

- 6.2.1 Within 2 days before Day 1 treatment of each cycle (for either chemo regimen):

- 6.2.1.1 History and physical exam

- 6.2.1.2 Vital signs (blood pressure, respiratory rate, height, weight)

- 6.2.1.3 Complete blood count (CBC) with differential and platelets.

- 6.2.1.4 Serum chemistries: liver enzymes (AST, ALT, alkaline phosphatase), blood urea nitrogen (BUN), creatinine, electrolytes (sodium, potassium, chloride, calcium, bicarbonate), total protein, albumin, total bilirubin, and glucose.

- 6.2.1.5 Adverse Event Assessment

6.3 Arm 2, Adjuvant Chemoradiation: Evaluations for patients deemed lymph node positive at time of surgery and treated with postoperative chemoradiation:

- 6.3.1 While on chemotherapy alone, within 2 days before Day 1 treatment of each cycle:

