15.0 APPENDIX I: SCHEDULE AND FLOW OF EVALUATIONS

15.1 ARM 1: Node-Negative, Adjuvant Chemotherapy.

Study Procedures	Screening & Baseline (1)	Arm 1: Cycle 1 (6)	Arm 1: Cycle 2 (6)	Arm 1: Cycle 3 (6)	Post-Treatment Surveillance, every 3 months (7)
Informed Consent	X				
History & Physical Exam; Vitals (2); ECOG PS	X	X	X	X	X
CBC + differential + platelets	X	X	X	X	X
CMP: Serum Chemistries (3)	X	X	X	X	X
AE Assessment		X	X	X	X
Pregnancy Test	X				
Tumor for genetic profile (4)	X				
Imaging (5)	X				X
Chemo, Adjuvant		X	X	X	
Survival Status, Recurrence					X

1. Screening procedures must be obtained within 28 days registration, with the exception of radiographic studies and tumor samples for baseline profiles.
2. Vital signs includes blood pressure, respiratory rate, height, and weight.
3. Serum chemistries to include: liver enzymes (AST, ALT, alkaline phosphatase), blood urea nitrogen (BUN), creatinine, electrolytes (sodium, potassium, chloride, calcium, bicarbonate), total protein, albumin, total bilirubin, glucose.
4. Tumor samples from diagnostic biopsy (before neo-adjuvant chemo) and surgery (after neo-adjuvant chemo) should be obtained (after subject consents to participate).
5. Can be either (1) CT of the chest with contrast and CT of the abdomen/pelvis with and without contrast, or (2) PET/CT from the skull base to mid-thigh. Baseline imaging must be after surgery, and within 42 days of starting adjuvant chemotherapy.
6. Procedures are to be repeated at the beginning of each cycle and can be assessed up to 2 days in advance of D1 for each cycle. These cycles are 14 days long if FOLFOX used and 21 days long if CAPEOX used.
7. Three month interval begins from the end of completion of chemotherapy, and continues until 36 months after surgery (unless patient comes off study, per Section 6). These assessments can be +/- 14 days from planned date. Imaging assessments during follow-up can occur every 3-6 months, per investigator's standard practice. If subject has disease recurrence, follow-up will stop.

15.2 ARM 2: Node-Positive, Adjuvant Chemoradiation.

Study Procedures	Screening & Baseline (1)	Arm 2: Chemo alone, Cycle 1 28-day cycle (6)	Arm 2: ChemoRT, 5 weeks Schedule is for each week					Arm 2: Chemo alone, Cycle 2 28-day cycle (6)	Arm 2: Chemo alone, Cycle 3 28-day cycle (6)	Post-Treatment Surveillance, every 3 months (7)
			W 1	W 2	W 3	W 4	W 5			
Informed Consent	X									
History & Physical Exam; Vitals (2); ECOG PS	X	X	X	X	X	X	X	X	X	

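### The exploratory gene-expression comparison reads nodal status at surgery as response to chemotherapy, but the plan neither requires nor records nodal stage before chemotherapy

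*Combined protocol and SAP*

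**What the plan says.** Synopsis 2.2 sets the correlative objective "using presence of nodal involvement at time of surgery as an indicator of response". Section 4.3.1 makes the indicator binary: "These differences will be correlated for any response in tumor, i.e., node positive versus node negative". The background in 3.1 gives the reasoning. Patients with a good outcome are "those whose tumors responded well, with the absence of nodal involvement upon dissection", and the majority needing another approach are those "who have an inadequate response to preoperative chemotherapy (i.e., who remain node-positive at surgery". The idea of remaining node positive presumes that nodes were involved at the start.

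The passages that could supply a starting point do not:

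- **Eligibility (5.1, item 1):** "Must have pathologically-proven adenocarcinoma of the stomach or gastroesophageal (GE)-junction, stage M0". There is no N-stage criterion.
- **Baseline evaluation (6.1.5):** "Nodal disease will be classified into one of two categories", namely "lymph node negative, where no nodes are involved with tumor, or lymph node positive, where one or more nodes are involved with tumor". This comes from the pathologic evaluation that decides the arm.
- **Imaging (Appendix I, footnote 5, both arms):** "Baseline imaging must be after surgery, and within 42 days of starting adjuvant chemotherapy".
- **Registration (7.0):** patients are reviewed for eligibility and registered only after surgery.
- **Analysis (10.0):** a paired t-test and multiple comparisons are named, with no stratification, adjustment or restriction by baseline nodal stage.

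Section 9.0 calls the work exploratory and sees it as something later studies could develop into a predictor of chemotherapy response.

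**The concern.** Nodal status at surgery reflects both where the patient started and what chemotherapy did. The plan measures expression before and after chemotherapy but measures nodes only after. This allows two kinds of misclassification. A patient without nodal disease at any time counts as a responder. A patient whose nodal burden fell from many nodes to one counts as a non-responder.

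The inference in 9.0 is at stake. If expression change differs between node-negative and node-positive patients, the gene may mark sensitivity to chemotherapy or may simply mark earlier-stage disease. The planned data cannot separate the two, and a later study built on the result could pursue the wrong hypothesis.

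**Working it through.** **The plan's own figures.** The correlative study has no stated sample size, effect size or power, so there is nothing of its own to reproduce. Section 10.0 gives precision for completion rates. At p = 0.5 the 95% Wilson half-width is z / (2√(n + z²)):

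- n = 30: 1.96 / (2√33.84) = 16.8 points (stated maximum 17)
- n = 10: 1.96 / (2√13.84) = 26.3 points (stated maximum 26.5)

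These agree with the plan, but they concern the primary endpoint and the point here does not depend on them.

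**Inputs from the documents.** There are 40 patients in a 3:1 ratio, so 30 node positive and 10 node negative (10.0). The 25% node-negative share also appears in 3.2.

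**Input not in the documents.** Let b be the share of enrolled patients who were node negative before chemotherapy, assumed to stay so. It is shown over its whole possible range.

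- Share of node-negative patients who never had nodal disease: f = b / 0.25
- True nodal clearance among those node positive at baseline: (0.25 − b) / (1 − b)

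| b (assumed) | Never node positive, of the 10 | f | True clearance (apparent 25%) |
|---|---|---|---|
| 0% | 0 | 0% | 25% |
| 5% | 2 | 20% | 0.20/0.95 = 21.1% |
| 10% | 4 | 40% | 0.15/0.90 = 16.7% |
| 15% | 6 | 60% | 0.10/0.85 = 11.8% |
| 20% | 8 | 80% | 0.05/0.80 = 6.25% |
| 25% | 10 | 100% | 0% |

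**Direction of the bias.** For one gene, let R be the mean expression change in true nodal responders minus that in node-positive patients, and S the same difference for patients who never had nodal disease. The planned contrast estimates (1 − f)R + fS.

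- If S = 0, a true difference is diluted to (1 − f)R.
- If R = 0 and S ≠ 0, the contrast shows fS, an association due to stage alone.
- If S = R, there is no bias.

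Nothing in the documents fixes f or S, so neither size nor direction is known.

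**Illustration only, with S = 0 assumed.** Take R = 1 SD, 10 versus 30 patients, one gene, two-sided 5% and no multiplicity correction. The standard error is √(1/10 + 1/30) = 0.365 SD. Approximate power is Φ((1 − f)/0.365 − 1.96): 78% at f = 0, 59% at f = 20%, 38% at f = 40% and 19% at f = 60%.

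**Precision of a restricted analysis.** The 95% half-width is 1.96√(1/n₁ + 1/30) SD: 0.72 with 10 node-negative patients, 0.78 with 8 and 1.04 with 4. This keeps all 30 node-positive patients and ignores the up to 10% of patients (4 of 40) whose paired specimens may be unassessable under 10.0.

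**The case against.** The strongest reply is that the plan claims little. The objective is to explore a potential correlation, no decision rule rests on it, and 9.0 leaves prediction to future studies. Nodal status at surgery is a legitimate outcome in its own right; 3.3 treats nodal response as a surrogate for outcomes, and correlating expression with it needs no baseline N stage. The named test is a within-patient paired comparison, and in the whole cohort it is not biased by how nodal status is labelled. The binary rule in 6.1.5 suits its purpose of assigning the arm.

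All of this stands and limits the severity. It does not remove the point, because prognostic value does not make nodal status a measure of response, and 2.2, 3.1 and 4.3.1 use it as one.

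Two stronger readings are tempting. A reader might infer that a definite fraction of the responder group is misclassified and that any true difference shrinks by that fraction. The documents give no pre-chemotherapy node-negative share, and dilution also requires such patients to resemble non-responders in expression change. Expression is measured in tumour tissue, so a patient without nodal disease can still show a chemotherapy effect. A reader might also infer that the whole correlative study, or the trial, is compromised. Arm assignment and the feasibility endpoint need only nodal status at surgery, so that does not follow.

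**Conclusion.** The point holds for the between-group comparison of expression change by nodal status, read as response versus non-response. As written, the plan labels any patient without nodal disease before chemotherapy a responder and collects nothing that would identify such patients.

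The one size that follows from the documents is that, with about 10 node-negative patients expected, each such patient is 10% of the responder group. The number of such patients, and whether they dilute a true difference or create a spurious one, cannot be determined. The power figures are illustrative and rest on both assumptions: the value of f and S = 0. This is worth correcting in an exploratory secondary objective, but it is not a threat to the trial's main purpose.

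**What to change.** 1. In 2.2, 4.3.1, 9.0 and 10.0, describe the comparison as by nodal status at surgery, not as response versus non-response.
2. Add pre-chemotherapy clinical N stage as a data item, abstracted from existing records where documented, with missing values reported.
3. In 10.0, report expression change descriptively by surgical nodal status cross-classified by baseline clinical N stage.
4. Add an exploratory sensitivity analysis limited to patients clinically node positive at diagnosis.

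Formal adjustment should not be the main remedy, because about 10 node-negative patients across a gene panel cannot support it.

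The cost is one chart item and a few sentences, with no new visit, biopsy or imaging. The documents do not say that clinical N stage is available in the records; that is an assumption. The protocol does not standardise this staging. Clinical N stage is also an imperfect guide to true nodal involvement, so some misclassification will remain. The restricted analysis is likely to have fewer than 10 node-negative patients and will be very imprecise.
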